	
following conditions are met:
 
- Palpable spleen length below the costal margin that has been reduced by < 40% at the Week 4 visit relative to baseline.- Platelet count at the Week 4 blood draw is > 150,000/μL and platelet count has never been < 150,000/μL at a prior laboratory assessment while receiving INC424 (Figure 6-1).- ANC levels have remained \geq1000/μL since enrollment in the study. 
Additional dose increases beyond the week 4 dose escalation for patients who start on 15 – 20 mg BID of INC424 are permitted, at the discretion of the investigator, as follows:
 
- The patient must not have had a prior safety-related dose reduction.- The patient must have had a platelet count \geq 150,000/μL at every assessment since baseline.- The patient must have had ANC \geq 1000/μL at every assessment since baseline.- The dose increase may only be an increase of 5 mg BID.- The total dose may never exceed 25 mg BID. 
For those patients who start INC424 treatment at a dose of 5 mg BID, dose increases can be made, at the discretion of the investigator, as described below. The dose can be escalated 5 mg once a day starting at week 4, and thereafter no more than every two weeks ONLY if:
 
- The patient must not have had a prior safety-related dose reduction.- Platelet count remains \geq 50,000/μL since last lab scheduled visit.- ANC $>$ 1000/μL since last scheduled visit.- No dose reduction or interruption for safety occurred in the preceding weeks after the last planned visit.- The dose increase may only be an increase of 5 mg o.d. i.e., from 5 mg PO BID to 5 mg QAM and 10 mg QPM.- The total dose may never exceed 25 mg BID. 
Following a dose increase, platelet count and ANC levels should be assessed approximately 2 weeks after the dose adjustment. If a regularly scheduled Study Visit does not coincide with this required blood draw, an unscheduled Interim Visit should be held to collect samples for hematology.
 
Dose interruption or dose reduction (Section 6.2.2) is mandatory as follows for patients who start on dose of 15 – 20 mg BID:
 
Dosing must be held if platelet counts decline to < 50,000/μL (Grade 3 laboratory abnormality by CTCAE v. 3.0, or if ANC falls below 500/μL while receiving INC424.
 
Doses should be decreased for platelet count values < 125,000/μL as shown in Table 6-2 with optional restarting or resuming prior dose after recovery Section 6.2.3 In order to provide sufficient data to make dose adjustment decisions, it is recommended that hematology parameters be obtained at least weekly for platelet count <100,000/μL or ANC < 1000/μL and at least two times weekly for platelet count < 50,000/μL or ANC <500/μL.
 
Dose interruptions or dose reductions for patients starting INC424 5 mg BID: dose

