In the randomized period of the two pivotal studies in MF, COMFORT-I and COMFORT-II discontinuation due to adverse events, regardless of causality was observed in 11.3% of patients. The most frequently reported adverse drug reactions were thrombocytopenia and anemia. Hematological adverse reactions (any Common Terminology Criteria for Adverse Events [CTCAE] Grade) included anemia (82.4%), thrombocytopenia (69.8%) and neutropenia (16.6 %). Anemia, thrombocytopenia and neutropenia are dose related effects. The three most frequent non-hematological adverse reactions were bruising (21.6%), dizziness (15.3%) and headache (14.0%). The three most frequent non-hematological laboratory abnormalities were raised alanine aminotransferase (27.2%), raised aspartate aminotransferase (18.6%) and hypercholesterolemia (16.9%).

[figure not shown]
Long-term follow-up in patients with MF in the phase I/II study INCB 18424-251 and the COMFORT studies has shown that as expected, the numbers and proportions of adverse events (AEs) and serious adverse events (SAEs) have increased; however, no new safety signals have emerged. Additionally in patients with MF, the dose optimization strategy of dose reduction and occasional dose interruption for thrombocytopenia was successful in maintaining patients on therapy with only one patient on the ruxolitinib arm of each study discontinuing for thrombocytopenia; platelet transfusions occurred with low frequency, comparable to the control arms in the Phase III studies.

2 Rationale

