A standardized approach is to be taken for dosing adjustments and for safety and efficacy so that each patient is titrated to their most appropriate doses (see [Section 6.2](#)). Doses of INC424 are not to exceed 25 mg PO BID

Table 6-1 Dose and treatment schedule

Study drugs	Pharmaceutical form and route of administration	Dose	Frequency
INC424	Tablet for oral use	See Section 6.1.1 .	BID continuously

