6.2 Dose modifications

6.2.1 Dose increases of INC424

6.2.1.1 Dose modification for patients starting INC424 at a dose of 15 – 20 mg BID

[figure not shown]
6.2.1.1.1 Dose increases of INC424 at week 4

As indicated in [Section 6.1.1](#) Study Drug Dosing, the initial dose of INC424 will be determined by the Baseline platelet count. In order to optimize each patient's dosage, after the first 4 weeks of therapy, doses may be increased by 5 mg BID for patients who meet all of the following conditions:

- Palpable spleen length below the costal margin that has been reduced by LESS THAN 40% at Week 4 visit relative to Baseline.
- Platelet count at the Week 4 blood draw is $> 150,000/\mu\text{L}$ and platelet count has never been below $150,000/\mu\text{L}$ at a prior laboratory evaluation while receiving INC424. (See [Figure 6-1](#)).

Absolute neutrophil count (ANC) levels have remained at or above $1000/\mu\text{L}$ since enrollment in the study.

Figure 6-1 Dose increase strategies for patients starting on INC424 15 – 20 mg BID with inadequate responses after at least Week 4:

6.2.1.1.2 Dose increases beyond week 4

After Week 4 (month 1), dose increases of INC424 are allowed for those patients who exhibit an INCREASE in palpable spleen length. The rules for these optional dose increases are as follows:

- The dose increases may only occur if the platelet count and ANC data for that visit are available.
- The palpable spleen length for that Study Visit must show a 2 cm or greater INCREASE in length compared to the on-study nadir (lowest palpable spleen measurement during the study, including Baseline).
- The patient must NOT have had a prior safety-related dose reduction.
- The following platelet threshold have been met:
 - The patient must have had a platelet count $\geq 150,000/\mu\text{L}$ at every assessment since Baseline for those starting INC424 at a starting dose of 15 – 20 mg BID.
 - The patient must have had ANC $\geq 1000/\mu\text{L}$ at every assessment since baseline.
 - The dose increase may only be an increase of 5 mg BID.
 - The total dose may never exceed 25 mg BID.
 - Following a dose increase, platelet count and ANC levels should be assessed approximately 2 weeks after the dose adjustment. If a regularly scheduled Study Visit does not coincide with this required blood draw, an unscheduled Interim Visit should be held to collect samples for hematology.

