- Patients who underwent dose escalation at week 12 (Month 3) should return to the clinic for serum chemistries and hematology assessments.

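### The synopsis rule for dose increases after Week 4 in 15–20 mg BID starters omits the spleen-growth condition that Section 6.2.1.1.2 requires

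*Protocol*

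**What the plan says.** The protocol synopsis, under Dose, regimen, treatment, first gives a Week 4 escalation rule for patients starting at 15–20 mg BID. That rule has a spleen criterion: a reduction of less than 40% from baseline. A separate list then covers later increases: "Additional dose increases beyond the week 4 dose escalation for patients who start on" 15–20 mg BID "of INC424 are permitted, at the discretion of the investigator, as follows". The items are no safety-related reduction so far ("The patient must not have had a prior safety-related dose reduction"), a platelet floor, an ANC floor, a fixed step and a dose cap. No spleen criterion appears in this second list.

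Section 6.2.1.1.2 covers the same increases in the same patients. Its opening sentence confines them to patients whose palpable spleen length has increased. Its conditions include: "The palpable spleen length for that Study Visit must show a 2 cm or greater INCREASE in length compared to the on-study nadir", and "The dose increases may only occur if the platelet count and ANC data for that visit are available".

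Section 6.1.1 sets the general aim, referring to Section 6.2: "A standardized approach is to be taken for dosing adjustments and for safety and efficacy".

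**The concern.** Both texts are current and both read as operative dosing instructions. The synopsis prints a full list and leaves the decision to the investigator. That list does not refer to Section 6.2.1, although the same part of the synopsis cites Section 6.2.2 for reductions and Section 6.2.3 for restarts. A site working from the synopsis has no sign that a condition is missing.

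The missing spleen condition is the efficacy reason for the increase. Without it, the texts define different groups of patients who may go to a higher dose. Section 1.3.5 says of the drug: "Anemia, thrombocytopenia and neutropenia are dose related effects". Increases after Week 4 are also expected in practice, since Section 7.5.1.8 gives follow-up instructions for them: "Patients who underwent dose escalation at week 12 (Month 3) should return to the clinic".

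Two things are at stake. One is avoidable exposure to a higher dose in patients whose spleen has not regrown. The other is inconsistent conduct: Sections 12.2 and 12.10 allow no authorized deviations, so a site that follows the synopsis in good faith could breach Section 6.2.1.1.2.

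**Working it through.** No sample size, power or error rate is involved. The check is a side-by-side comparison, followed by the dose arithmetic.

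**Conditions for an increase after Week 4, 15–20 mg BID starters**

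| Condition | Synopsis | Section 6.2.1.1.2 |
|---|---|---|
| No earlier safety-related reduction | yes | yes |
| Platelets ≥ 150,000/µL at every assessment | yes | yes |
| ANC ≥ 1000/µL at every assessment | yes | yes |
| Step of 5 mg BID | yes | yes |
| Cap of 25 mg BID | yes | yes |
| Spleen ≥ 2 cm above on-study nadir | no | yes |
| That visit's platelet and ANC data available | no | yes |

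The count is 5 against 7, so 7 − 5 = 2 are missing. Both texts also ask for a blood count about two weeks after an increase. That is a follow-up action rather than a condition, and counting it would not change the difference of two. The data-availability condition is largely implied by the platelet and ANC floors, which leaves the spleen condition as the substantive gap.

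**Direction.** Every increase the section allows is also allowed by the synopsis. The reverse is not true.

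**Example.** A 15 mg BID starter has a baseline spleen of 10 cm and 7 cm at Week 4.
- Reduction at Week 4: (10 − 7)/10 = 30%, below 40%. With the blood-count conditions met, the dose goes to 20 mg BID.
- At Week 8 the spleen is 7 or 8 cm. Distance from nadir: 7 − 7 = 0 cm or 8 − 7 = 1 cm, both below 2 cm.
- With counts still qualifying, a step to 25 mg BID is open under the synopsis and closed under Section 6.2.1.1.2.

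**Room left under the cap.** Steps = (25 − current dose)/5, assuming the standard starting doses of Section 6.1.1.

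| Patient | Steps left | Extra dose |
|---|---|---|
| 15 mg starter, raised at Week 4 | (25 − 20)/5 = 1 | 40 to 50 mg/day: +10, 10/40 = 25% |
| 15 mg starter, not raised | (25 − 15)/5 = 2 | 30 to 50 mg/day: +20, 20/30 = 67% |
| 20 mg starter, not raised | (25 − 20)/5 = 1 | 40 to 50 mg/day: +10, 25% |
| 20 mg starter, raised at Week 4 | (25 − 25)/5 = 0 | none |

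If the platelet floor is read to include the baseline value, 15 mg starters with a baseline count from 100,000 to below 150,000/µL are barred under both texts.

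**Toxicity.** The phase I/II figures give a direction only. Section 1.3.4.1 reports Grade 3 thrombocytopenia in 3% at 15 mg BID and 23% at 25 mg BID, plus 6% Grade 4 at 25 mg BID. The synopsis background gives a smaller gradient for grade ≥ 3 in that study: 29% and 36%. Neither describes patients escalated after persistently good counts, so no excess rate can be derived.

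**The case against.** The best defence is that the intended rule can be found. The synopsis sends readers to Section 6.1.1 for the starting doses, and that section points to Section 6.2 for adjustments. Section 8.3.1.1 says palpated spleen length informs dose increases for lack of efficacy. Section 7.5.1.3 refers sites to Section 6.2.1.1 for the Week 4 increase. The synopsis also ties escalation to inadequate response, so it does not invite raising the dose of a good responder. A site that follows the section obeys both texts. On this view the synopsis is an incomplete summary of a rule stated properly elsewhere.

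Much of that stands. Section 6.2.1.1.2 is very probably the intended rule. But none of these references states precedence or supplies a spleen threshold after Week 4, and the synopsis list reads as complete. Figure 6-1 is not shown in the text available, so nothing is concluded from it; the synopsis cites it only for the Week 4 platelet condition.

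A second objection is that doses could differ between sites even if the texts matched, because these increases are optional. That is true of the choice to escalate. It does not explain why the set of patients who may be escalated should differ.

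Third, the 67% figure is an upper end. It needs two separate steps in a patient who was not raised at Week 4, and such patients mostly either had a spleen reduction of at least 40% or were left alone by choice. If the word "additional" in the synopsis means only patients already escalated at Week 4, just the single 20 to 25 mg BID step remains.

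Finally, the consequences for the analysis are slight, and that stands in full. The study is single-arm with no hypothesis test, dose changes are recorded, and the exclusions from the per-protocol set in SAP Section 2.1 do not involve dosing.

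**Conclusion.** The concern holds. For 15–20 mg BID starters, the synopsis list omits two of the seven conditions in Section 6.2.1.1.2, and one of them, spleen regrowth of at least 2 cm from nadir, changes who may be escalated. As written, the synopsis opens a route to a higher dose that the section closes.

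The affected group is narrow: platelets and ANC above their floors throughout, no safety-related reduction, and a current dose below 25 mg BID. The extra dose is 10 mg/day (25%) on the narrower reading and at most 20 mg/day (67%) on the wider one. The number of patients and any excess toxicity cannot be obtained from the documents. Recruitment ended on 31 December 2014, so only patients still on treatment are affected. The discrepancy should be corrected, but no endpoint or analysis set depends on it.

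This rests on reading the synopsis list as a complete set of conditions and on treating the two-week blood count as follow-up.

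**What to change.** Make Section 6.2.1.1.2 the single rule. Either add its two missing conditions (spleen at least 2 cm above the on-study nadir, and that visit's platelet and ANC results available) to the synopsis list, or replace the list with a reference to Section 6.2.1.1.2. Until the text is changed, write to sites stating that Section 6.2.1.1.2 governs increases after Week 4 for 15–20 mg BID starters.

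The cost is amendment or clarification wording. No new procedure is needed, because spleen length and blood counts are already taken at study visits.

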	
to independent or vice versa) will be tabulated with summary statistics.
 
Quality of Life Assessments
 
ECOG score will be summarized descriptively by visit. A shift summary including number and % of patients will be produced by visit for baseline vs. post-baseline scores.
 
Data from FACT-Lymphoma (version 4) Scores will be analyzed in the sum scores. Change and % change from baseline to each scheduled visit will be calculated. The treatment effect on FACT-Lymphoma Scores over time will be estimated using repeated measurements analysis.
 
Data from FACIT Scores will be analyzed in the sum scores. Change and % of change from baseline to each scheduled visit.
 
Time to first improvement will be estimated for ECOG performance score and for selected scales for FACT-Lymphoma (version 4) and FACIT scale according to minimally important difference (MID).
 
[REDACTED]
 
[REDACTED]

Interim analysis (IA)	
An interim analysis will be performed to closely monitor safety, and ensure an appropriate risk/benefit ratio in the patient population with low platelet counts, between 50,000 and <100,000/μL /μL. In order to adequately assess the risk/benefit ratio, this analysis will also be performed on a non-low platelet population (patients with baseline platelet count \geq100,000/μL), which will be further detailed in analysis plan, who will serve as an internal reference population. This interim analysis will take place when 50 patients with low platelets have completed 6 months of treatment
 
Analyses will also be performed if needed to fulfill regulatory obligation, to comply with post-approval commitments or for publication purpose.

1 Background

[figure not shown]
INC424 phosphate is an inhibitor of the Janus kinase family of protein tyrosine kinases (JAKs) that is currently under development for treatment of primary myelofibrosis (PMF), post polycythemia vera myelofibrosis (PPV MF) and post essential thrombocythemia myelofibrosis (PET-MF). INC424 (ruxolitinib, Jakafi®) was approved by the FDA on 16 November 2011, and approved by the EMA on 31 August 2012, for the treatment of intermediate or high-risk myelofibrosis, including primary myelofibrosis, post-polycythemia vera myelofibrosis and post-essential thrombocythemia myelofibrosis.

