8.3.2.2 FACIT-Fatigue Scale

The FACIT Fatigue (FACIT-F) questionnaire was developed to assess fatigue associated with anemia and includes 13 fatigue-related questions (FACIT fatigue). The responses to the 13

[figure not shown]
items in the questionnaire are each measured on a 4-point Likert scale ([Cella et al 1993](#)). Thus, the total score ranges from 0 to 52. High scores represent less fatigue. The FACIT Fatigue Scale has been validated in the general population, in patients with cancer and in patients with RA. In patients with cancer, the FACIT Fatigue Scale showed excellent internal consistency and reliability and differentiated patients by hemoglobin level and patient-related performance status ([Chandran 2007](#)).

[Cella et al \(2002\)](#) determined the minimally important difference (MID) of the FACIT-Fatigue scale to be 3 points.

Subjects will complete this assessment at Baseline and at each visit as indicated in [Table 7-1](#).

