1.1 Study design

This is a phase IIIB, multicenter, single-arm, open-label expanded access study intended to provide additional data on the safety and efficacy of INC424 in patients with PMF or PPV MF, or PET-MF who have either received prior treatment or who have never received treatment.

Patients will be screened within four weeks prior to the first dose of INC424.

Baseline evaluations will be performed within a week of the first dose of INC424.

Visits will occur on a monthly basis for the first 3 months, then every 3 months thereafter and at study discontinuation.

In this document, study drug refers to INC424.

For this study, study drug will be administered continuously. All patients will be treated with oral INC424 at a dose of 5 - 25 mg (dose based on baseline platelet count) BID until one of the following occurs: disease progression; transplant; unacceptable toxicity; death; discontinuation from the study for any other reason; withdrawal of consent; physician decision; until the study drug becomes commercially available in each participating country or until 24- months after last patient first visit (LPFV), or the project is discontinued, whichever occurs first.

If it is determined at any study visit that the patient will discontinue study drug that day, then that study visit will be the end-of-study visit, and the end-of-study visit procedures will be followed. (Refer to protocol section 7.6.2)

An interim analysis planned for this study will take place when 50 patients with low platelets will have completed 6 months of treatment. Additional analyses may also be performed if needed to fulfill regulatory obligation or publication purpose.

The final analysis will be performed after all patients have either completed the study or have been prematurely discontinued from the study.

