Change in FACIT Fatigue scores:

Data from FACIT-Fatigue scores will be analyzed in the sum scores. Change and percent change from baseline to each scheduled visit when the FACIT Fatigue scores were collected will be calculated with the data collect from the last visit prior to and at Day 1 as the baseline. The scores will be summarized descriptively by visit.

Responder Analysis and Time to first improvement:

The proportion of patients showing improvement will be estimated for ECOG performance score, the three FACT Lym sum scores and one subscale LymS and FACIT Fatigue scale.

The improvement (i.e. the responder) will be defined by the upper limit of the MID. Patients with the best possible score at baseline will be excluded from this analysis because their HRQoL cannot be further improved.

Additionally, the proportion of patients achieving response (HRQoL) by the lower limit of MID will be presented by visit.

Responders and non-responders for a PRO endpoint will be defined based on change from baseline scores using pre specified cutoff points. Patients with an improved PRO score compared to baseline, for which the magnitude of the change was at least the cutoff value, will be classified as responder; otherwise, non-responder.

To define PRO responder, the cutoff points are chosen based on minimum important difference from literature as listed in the following table.

PRO Score	Range	MID	Responder Cutoff
FACT -G total	0-108	3-7 ^c	7
ECOG performance status	0-5	NA	1
FACT-Lym subscale	0-60	2.9-5.4 ^d	5.4
FACT-Lym TOI	0-116	5.5-11 ^d	11

PRO Score	Range	MID	Responder Cutoff
FACT-Lym Total	0-168	6.5-11.2 ^d	11.2
FACIT - Fatigue	0-52	3	3

^a Kvam et al., 2010; ^b Osoba et al., 1998; ^c Webster et al., 2003; ^d Carter et al., 2008.

The median time to first improvement will be estimated using Kaplan Meier method for ECOG performance score, the three FACT Lym sum scores and one subscale LymS and FACIT Fatigue scale. The time to improvement event will be determined based on upper bound of the MID. The time to improvement is calculated from the date of first study drug administration.

Patients, who prematurely discontinued the study drug, will be censored at the date of their last assessment before study discontinuation.

Patients with no baseline score will be censored at study day 1.

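### Kaplan-Meier time to first improvement censors patients who stop drug or die unimproved, so it overstates the share improving and can give a median when fewer than half improved

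*Protocol*

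**What the plan says.** The protocol names the endpoint but not the method. The synopsis (Quality of Life Assessments) states that "Time to first improvement will be estimated for ECOG performance score and for selected scales for FACT-Lymphoma (version 4) and FACIT scale", and section 11.6.5 plans the proportion improved beside it. Neither gives an estimator, a censoring rule or an event rule beyond the minimally important difference (MID).

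SAP 3.4.4, under the responder and time-to-improvement heading, supplies the rest:

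- Estimator: "The median time to first improvement will be estimated using Kaplan Meier method for ECOG performance score", the three FACT-Lym sum scores, the lymphoma subscale and FACIT-Fatigue, counted from first dose.
- Event: "The time to improvement event will be determined based on upper bound of the MID". The tabulated cutoffs are 7 for FACT-G, 5.4 for the lymphoma subscale, 11 for the TOI, 11.2 for FACT-Lym total, 3 for FACIT-Fatigue and 1 level for ECOG. A responder is a patient with an improved score "for which the magnitude of the change was at least the cutoff value, will be classified as responder; otherwise, non-responder"; no second assessment has to confirm it.
- Censoring: "Patients, who prematurely discontinued the study drug, will be censored at the date of their last assessment before study discontinuation". Also, "Patients with no baseline score will be censored at study day 1".
- Death: no rule for this endpoint. SAP 1.1 lists, among the ends of treatment, "disease progression; transplant; unacceptable toxicity; death; discontinuation from the study for any other reason; withdrawal of consent; physician decision", so death comes under the censoring rule by implication. The same list adds commercial availability of the drug and 24 months after last patient first visit (LPFV).

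Table 7-1 of the protocol schedules both questionnaires at baseline and Weeks 4, 12, 24 and 48. ECOG is rated at every on-treatment visit after Day 1, including those from Week 60 onwards.

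**The concern.** Kaplan-Meier estimates the share with an event correctly when a censored patient's later chance of the event is like that of the patients still followed. That is reasonable for someone who leaves because the drug has reached the national market. It is not reasonable for someone who has died, and is doubtful for someone who stopped for progression or toxicity. The curve answers what would have happened had these patients stayed on drug. A reader will take it as what did happen.

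Quality of life is a stated secondary objective. In patients without splenomegaly, protocol section 3.3.2 rests efficacy on patient-reported outcomes. With no control arm, the level of the curve and its median are themselves the result, so an upward shift is not offset by the same shift in a comparator.

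**Working it through.** The documents state no event rate, median or overall discontinuation rate for this endpoint, so there is no figure of the plan's own to reproduce.

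**Step 1. Small example.** Of 100 patients, 40 improve at Week 4. Of the 60 who have not, 30 stop before Week 12. Of the 30 left, 6 improve at Week 12.

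- Kaplan-Meier survival = (1 − 40/100) × (1 − 6/30) = 0.60 × 0.80 = 0.48, so 52% are estimated as improved and the median is Week 12.
- Observed improved = 40 + 6 = 46 of 100.

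This is a heavy loss. If 10 stop instead of 30 and the Week 12 rate stays at 20%, 50 × 0.20 = 10 improve: observed 50%, Kaplan-Meier still 52%. With 6 stopping, 54 × 0.20 = 10.8: observed 50.8% against 52%.

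**Step 2. The questionnaire schedule.** Visits are at Weeks 4, 12, 24 and 48. Assume the same chance h of first improvement at each visit among those still at risk, and a loss fraction d by Week 48 accruing exponentially, so that the fraction retained at week w is (1 − d)^(w/48).

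- Kaplan-Meier share improved = 1 − (1 − h)^4. Setting this to 50% gives h = 1 − 0.5^(1/4) = 0.1591.
- Observed share improved = Σ h × (1 − h)^(v−1) × (1 − d)^(w_v/48), with v = 1 to 4.

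For d = 40% the retained fractions are 0.9583, 0.8801, 0.7746 and 0.6000, and the still-unimproved fractions are 1, 0.8409, 0.7071 and 0.5946. The sum of products is 0.9583 + 0.7401 + 0.5477 + 0.3568 = 2.6029, and 0.1591 × 2.6029 = 41.4%.

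| Lost by Week 48 (assumed) | Kaplan-Meier improved | Observed improved | Gap (points) | Observed when Kaplan-Meier is 55% |
|---|---|---|---|---|
| 10% | 50% | 48.0% | 2.0 | 52.8% |
| 20% | 50% | 45.9% | 4.1 | 50.6% |
| 30% | 50% | 43.7% | 6.3 | 48.2% |
| 40% | 50% | 41.4% | 8.6 | 45.8% |
| 50% | 50% | 39.0% | 11.0 | 43.1% |

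A median reported with under half improved therefore needs a Kaplan-Meier value in a limited window: roughly 50% to 54% at 20% loss, widening to about 50% to 60% at 40% loss.

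The table counts all loss as non-administrative. Any part that is administrative belongs in censoring and does not add to the overstatement.

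**Step 3. Single unconfirmed crossings.** The cutoff is the upper MID bound, but for FACIT-Fatigue the protocol (8.3.2.2) says the cited work "determined the minimally important difference (MID) of the FACIT-Fatigue scale to be 3 points", so upper bound and MID coincide. With no true change, four post-baseline scores sharing one baseline, and an assumed between-patient SD of 10 to 12.5 with reliability 0.80 to 0.95, 47% to 69% of patients reach 3 points at least once. Requiring the crossing at two consecutive visits lowers this to 18% to 36%.

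For ECOG, assume a 5% to 10% chance per visit of a one-level better rating. Over 10 visits, independence gives 1 − 0.95^10 = 40% to 1 − 0.90^10 = 65%. Allowing correlation between visits (beta-binomial, assumed 0.2 to 0.4) gives 16% to 43%.

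The other scales are less exposed. At high assumed reliability the figure is as low as 5% for the lymphoma subscale and 8% for the TOI.

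**The case against.** The strongest reply is that the result would not be hidden. The SAP reports the proportion improved at the same cutoffs beside the median, the proportion by visit at the lower MID bound, change from baseline by visit, questionnaire completion rates and an ECOG shift table. A median contradicted by a proportion below one half would be visible in the same report. The SAP also uses the stricter MID bound and leaves patients at the best possible baseline score out of the responder analysis. All of this stands and limits the harm. It does not correct the curve or the median, and the SAP does not say how a reader should reconcile the two figures.

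The second reply is that the loss may be small. The nearest figure in the documents is the 11.0% discontinuation for adverse events in COMFORT-I (protocol 1.3.5). It leaves out death, progression and other reasons, so it is a low-end reference. At 10% to 20% loss the gap is only about 2 to 4 points. That also stands.

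A reader might go further and infer that many of the reported improvements would be chance crossings. The documents do not support this. They give no SD, reliability or ECOG misgrading rate; the ranges above are assumptions and differ widely between scales. A reader might also object that ECOG and questionnaire times are not comparable because ECOG has more ratings, but no section plans to compare them.

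**Conclusion.** The point holds for the estimator and the censoring rule. As written, SAP 3.4.4 overstates the share of patients who improve on treatment, and can report a median when fewer than half improved. With Kaplan-Meier at 50%, the overstatement is about 2 to 4 points at 10% to 20% loss by Week 48 and about 6 to 11 points at 30% to 50% loss. This rests on assumed loss rates, an equal chance of improvement at each visit, and loss that is not administrative. The case is strongest for death, and next for progression and toxicity. That deaths are censored is an inference from the end-of-treatment list; the SAP does not say so.

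Counting a single crossing is a lesser matter: a sensitivity to be shown, mainly for FACIT-Fatigue and ECOG, and not evidence that the improvements are spurious. The endpoint is secondary and descriptive, so no hypothesis test is affected. The change is still worth making, because the figure would otherwise not describe what happened to the patients treated.

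**What to change.** In SAP 3.4.4:

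1. Estimate the cumulative incidence of first improvement, with death, or stopping study drug for a non-administrative reason, before improvement as the competing event. Report a median only if that curve reaches 50%.
2. State the rule for death explicitly.
3. Keep censoring for administrative stops: drug commercially available, or 24 months after LPFV. Treating these as competing events would make the improvement rate depend on national launch dates.
4. Report the cumulative percentage improved by Weeks 4, 12, 24 and 48.
5. As supportive analyses only, add a version in which improvement is confirmed at the next assessment, and an ECOG version limited to the questionnaire visits.

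Item 5 should not replace the main analysis. With questionnaires at Weeks 4, 12, 24 and 48, confirmation means persistence for 8, 12 or 24 weeks. That is durable improvement rather than first improvement: a patient who improves and then misses or stops before the next visit drops out of the numerator, and a first improvement at Week 48 cannot be confirmed. Restricting ECOG visits discards collected data.

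The cost is SAP wording and programming. Protocol 6.2.6 already has the date and specific reason for stopping recorded in the eCRF; the SAP needs to say which recorded reasons count as administrative. The downside is extra programming and slightly lower reported improvement rates.
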